A feasibility clinical trial conducted by our group tested the ReCognitionVR cognitive interventions on older and young healthy volunteers (Appendix A. Final Study Report). The results of this study showed that ReCognitionVR-based cognitive exercises were feasible, acceptable, and tolerable by older healthy subjects. In stage 2 of our research study, we want to evaluate the safety, feasibility, acceptability, and tolerability of VR-based cognitive exercises in 60-year-old or older patients following abdominal surgery admitted to the surgical floor at Houston Methodist Hospital (HMH). Our premise is that VR-based cognitive stimulation software will allow the controlled delivery of structured cognitive exercises focusing on orientation, attention, memory, and executive functions. The system will allow customized frequency and duration of cognitive exercises based on the users' difficulty level in a delightfully relaxed-environment with beach wave sounds.

Hypothesis:

We will test the hypothesis that the test population will find ReCognitionVR-based cognitive exercise safe, feasible, acceptable, and tolerable.

2. Purpose of the Study / Objectives

This study aims to assess the feasibility, acceptability, and safety of using ReCognitionVR-based software in older surgical patients. Results from this study will be used to inform the design of a future study in critically ill hospitalized patients at risk for delirium.

The question that drives this study is:

In surgical floor patients, what is the safety and feasibility of using the ReCognition VR-based cognitive exercise, and what is the acceptability and tolerability of the exercise?

OBJECTIVES AND ENDPOINTS

OBJECTIVES	ENDPOINTS	JUSTIFICATION FOR ENDPOINTS
Primary		
The primary objective of this study is the safety of VR-based cognitive stimulation exercises for older surgical patients.	The primary endpoint is the proportion of treatment-emergent adverse events (TEAE) in each group (experimental and control).	 To assess tolerability of ReCognitionVR-based cognitive stimulation exercises. Adverse events (e.g., cybersickness) will assess tolerability

Page 2 of 21

OBJECTIVES	ENDPOINTS	JUSTIFICATION FOR ENDPOINTS
		during engagement through exercise provided by ReCognitionVR games.
Secondary		

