The study is a single-center, prospective assessment of the feasibility, acceptability, and usability of ReCognition VR -based simulated cognitive stimulation to improve attention and focus in surgical patients.

Sample size: We will enroll 30 participants: 15 participants who are ≥60 years of age with traditional orientation methods and 15 participants who are ≥60 years of age and receive ReCognitionVR-based cognitive exercises.

Justification of sample size: The study is a feasibility study expecting that 70% of participants in the study intervention group will complete 20 minutes of the ReCognitionVR-based exercise, where each group will be evaluated separately. Descriptive statistics will be used to summarize the findings; 15 participants in each group will be recruited. The intent is that this study will provide information for a larger, subsequent clinical trial of patients ≥60 years old at risk for delirium.

Data and measures to be taken:

The endpoints for this feasibility study are:

Primary Objective:

Safety/Tolerability: We will examine measures that can inform on the safety of the experience to be used in the subsequent clinical trial. The measures are:

- 1. Mean change from pre to 10 minutes of the ReCognition VR-based exercise in:
 - a. SpO2
 - b. RR
 - c. Blood pressure (Mean BP, Systolic BP, and Diastolic BP)
- 2. Mean change from pre to end of the ReCognition VR-based exercise in:
 - a. SpO2
 - b. RR
 - c. Blood pressure (Mean BP, Systolic BP, and Diastolic BP)

Secondary Objectives:

Feasibility: 70% of participants in each group will complete 20 minutes of use of the ReCognition VR-based software (a binary outcome).

Acceptability: We will measure the acceptability and usability of the experience based on the proportion of participants with a SUS score >35.

VR-games Accuracy: We will report on the proportion of participants who complete the game without any user errors and the number of attempts each participant uses to complete the game.

Page 6 of 21

Exploratory Objective:

Delirium: We will assess delirium using CAM tool⁶ or the 4 A's test⁷. Delirium is defined as any positive CAM Score or/and score of 4 or above on the 4 A's test for 72 hours after study interventions.

Accessing data from medical records:

Medical records of the potential study subjects will be reviewed for medical history for the inclusion and exclusion criteria described below in section 10.

Data analysis plan:

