We will report the demographic variables of age, sex, race, and ethnicity for each group and the clinical characteristics and will review the patient's medical records for body mass index, history of hypertension with active management, drinking status, smoking status, ASA status, preexisting medical co-morbidities. If not found in the medical record, we will obtain this information.

[figure not shown]
The results of this study will be reported using descriptive statistics. Continuous variables will be reported as means with standard deviation or medians and interquartile range contingent on the normality of the distribution. Categorical variables will be reported using Chi-square or Fisher's exact test, as appropriate.

5. Study Intervention

- 1. Older patients (≥ 60 years old) scheduled to undergo abdominal surgeries (open or laparoscopic or robotic assisted), small bowel and large bowel surgery; cholecystectomy; Whipple procedure; pancreatectomy; splenectomy at HMH will be invited to participate.
- 2. We will screen patients for inclusion and exclusion criteria and will assign a screening number.
- 3. After signing informed consent, participants will be enrolled in the study and randomized using computer-generated randomization software to traditional orientation method (control) or ReCognitionVR-based cognitive exercises (experimental).
- 4. The experimental group will watch a video on using VR technology, placement of a VR headset, and assessment of baseline cognitive function using the Mini-Cog screening tool.
- 5. All participants will have a frailty screening assessment.9

Page 7 of 21

- 6. The Mini-Cog screening tool will assess the patient's cognitive status of all participants. (Appendix D)⁸
- 7. The experimental group will receive a 3D- ReCognitionVR-based simulated cognitive exercise program targeting attention, organizing thinking, and motor activities using VR games. The participant will receive study intervention after arrival to the room from the operating room, free of residual anesthesia, by measuring the Richmond Sedation Scale (RASS)- Appendix E^{10} score of 0.

- 8. The detail of the software as follows:
 - 3-D Recognition Virtual Reality-Based Simulation Sessions Program: Software Platform:

The VR platform will consist of

Page 8 of 21

- The VR headsets manufactured by the Oculus Quest 2 glasses (Facebook Inc., USA) with stereoscopic vision and stereo sound will be used to show the virtual world to participants.

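### The only method named for comparing categorical outcomes is a test of no difference, which cannot support the stated safety hypothesis; no margin, interval or between-arm estimate is planned

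*Combined protocol and SAP*

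**What the plan says.** The Hypothesis paragraph before section 2 reads: "We will test the hypothesis that the test population will find ReCognitionVR-based cognitive exercise safe, feasible, acceptable, and tolerable". The objectives table in section 2 makes safety the primary objective and states: "The primary endpoint is the proportion of treatment-emergent adverse events (TEAE) in each group". Section 5 randomises participants to VR exercise or traditional orientation, and section 4 plans 15 in each arm.

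The data analysis plan in section 4 begins its statistical part with "The results of this study will be reported using descriptive statistics". It goes on to continuous variables (mean and SD, or median and IQR) and then says "Categorical variables will be reported using Chi-square or Fisher's exact test, as appropriate". That sentence names no outcome, null hypothesis or alpha.

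Two other places bear on the primary endpoint. Section 14 says adverse events will be reported as the proportion of participants who develop them. Section 4, under Primary Objective, introduces its list with "We will examine measures that can inform on the safety of the experience" and then gives mean changes in SpO2, respiratory rate and blood pressure; the TEAE proportion is not in that list.

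No section gives a maximum acceptable TEAE rate, a margin, a confidence interval or a between-arm difference.

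**The concern.** Chi-square and Fisher's exact test are significance tests, not ways to report a proportion. Applied to two arms, their null hypothesis is that the event rates are equal. Rejecting it would suggest a difference; failing to reject it says only that the data could not exclude equality. The plan therefore sets a hypothesis of safety beside a method that cannot support it, and offers no other criterion.

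At stake is how the primary result can be read. Fifteen per arm gives little power, so a non-significant p-value is a common outcome even when VR raises the event rate materially. The study is meant to inform a larger trial. For that purpose, arm-specific rates and their difference, each with its uncertainty, are more useful than a p-value, and the randomised control arm adds little without them.

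**Working it through.** **Inputs from the documents**
- 15 per arm, 30 in total (section 4).
- Pilot adverse event rates in healthy volunteers, all of whom used VR (section 3): 3/15 and 1/15. The stated percentages reproduce: 3/15 = 20%, 1/15 = 6.67%.
- The 15 per arm cannot be reproduced by a formula. The justification rests on an expected 70% completion and gives no alpha, power, effect size, margin or precision target.

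**Assumptions**
- Two-sided alpha of 0.05; none is stated.
- True event rates as listed below. The 6.7% and 20% are borrowed from the pilot. No rate for postoperative controls is given, so higher control rates are also shown.

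**Step 1. How often the test is non-significant.** With X (VR) and Y (control) binomial on 15 each,

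P(non-significant) = 1 − Σₐ Σ_b P(X=a) · P(Y=b) · 1[p(a,b) ≤ 0.05],

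summed over all 16 × 16 outcomes.

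| Control vs VR rate | Fisher | Uncorrected chi-square |
|---|---|---|
| 6.7% vs 6.7% | 99.8% | 98.9% |
| 6.7% vs 20% | 93.5% | 84.8% |
| 20% vs 40% | 88.8% | 76.7% |
| 50% vs 70% | 90.3% | 80.5% |
| 6.7% vs 30% | 77.5% | 61.8% |
| 6.7% vs 40% | 55.3% | 37.0% |
| 6.7% vs 60% | 16.1% | 6.4% |

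Fisher reaches 80% power only at about 0% vs 41%, 6.7% vs 58% or 20% vs 76%.

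**Step 2. What Fisher needs to see.**
- Against 0/15 controls: 5/15 gives p = 2·C(15,5)/C(30,5) = 2·3003/142506 = 0.042; 4/15 gives 2·1365/27405 = 0.100.
- Against 1/15 controls: 7/15 gives p = 0.035; 6/15 gives p = 0.080.

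**Step 3. What a non-significant result leaves open.** Take 4/15 VR against 1/15 control.
- Fisher: p = 2·[C(15,4)·15 + C(15,5)]/C(30,5) = 2·(20475 + 3003)/142506 = 0.33.
- Difference: 0.267 − 0.067 = +0.200.
- Wilson 95% limits: 0.109 to 0.520 for 4/15; 0.012 to 0.298 for 1/15.
- Newcombe lower limit: 0.200 − √[(0.267−0.109)² + (0.298−0.067)²] = 0.200 − 0.280 = −0.080.
- Newcombe upper limit: 0.200 + √[(0.520−0.267)² + (0.067−0.012)²] = 0.200 + 0.259 = +0.459.

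So p = 0.33 goes with an interval of −8 to +46 points. Even 1/15 against 1/15 (p = 1.00) has an interval of −24 to +24 points.

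**Step 4. Best case in one arm.** With 0/15 events the exact two-sided 95% upper limit is 1 − 0.025^(1/15) = 21.8%.

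**The case against.** The strongest reply is that this is a 30-patient descriptive feasibility study with one loosely worded sentence. That sentence does not name TEAEs, and the analysis plan opens with demographic and clinical characteristics, to which it also applies. Section 14 plans a plain proportion for adverse events, and the pilot's adverse events were given as counts and percentages without a p-value. This stands in part: the test reaches the primary endpoint only through general wording, and a reader should not infer that a p-value is the planned primary result. The gap remains, because section 14 adds neither an interval nor a between-arm difference.

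A reader might also infer that the sponsor will declare VR safe if p exceeds 0.05. The documents do not say so. The risk is that the plan leaves that reading open while offering no other criterion for its hypothesis.

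Nor is non-significance a foregone conclusion. It depends on the true excess, and it is less frequent with chi-square, which could be the test chosen if event counts are higher: 9/15 vs 3/15 gives p = 0.025 by uncorrected chi-square and 0.060 by Fisher. Control rates over 72 hours after abdominal surgery could well exceed the pilot's.

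Finally, the phrase "where each group will be evaluated separately" might be taken to contradict the between-group test. It belongs to the sample-size sentence about completing 20 minutes of VR and is not a general analysis rule, so no weight is put on it here.

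It is fair to add that intervals at this size are wide: about 54 points in the example above. That is a reason to show the uncertainty.

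**Conclusion.** The point holds. The plan's one rule for categorical variables is a test whose null is no difference. It stands beside a stated hypothesis of safety, with no margin, interval or between-arm estimate anywhere in the documents. A non-significant Fisher result is likely unless the excess is very large: about 93% of trials at 6.7% vs 20%, 89% at 20% vs 40%, 78% at 6.7% vs 30% and 55% at 6.7% vs 40%. Such a result would be no evidence of safety.

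These frequencies rest on an assumed two-sided alpha of 0.05 and on illustrative rates. The reasoning that a test of no difference cannot establish safety does not depend on them. The point also takes the objectives table at its word that TEAE is the primary endpoint, although the Primary Objective list in section 4 shows vital-sign changes instead.

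The flaw is in the analysis plan and can be corrected before the data are analysed.

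**What to change.** Replace the categorical-variable sentence in section 4 with:

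> Categorical outcomes will be reported as n (%) with exact 95% CIs by randomised arm. For the proportion of participants with any TEAE, the between-arm risk difference will be given with a 95% Newcombe CI. No significance test will be used to conclude safety.

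Restate the safety part of the Hypothesis paragraph as an estimation objective: to estimate the TEAE proportion in each arm and the difference between arms.

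Apply the difference only to events ascertained over the same period in both arms. The adverse event review in the Schedule of Activities, which runs to 72 hours, can serve if it is carried out in both arms; the plan should state when that period starts for controls. The section 14 events defined within 5 minutes of starting VR should be reported for the VR arm alone. Controls have no such window, so a difference would be taken against a structural zero.

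The cost is wording only, with no added participants, visits or measurements. The downside is that the intervals will be wide and the reported conclusion less favourable than a statement of no significant difference.

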- Motion Sensor
- Flat Screen TV with Software

The VR headsets manufactured by the Oculus Quest 2 glasses (Facebook Inc., USA) with stereoscopic vision and stereo sound will be used to show the VR to study participants. After headset placement, the study participants will be able to follow instructions provided by virtual nurse AVATAR. The participants will receive low cognitive load exercises based on virtual reality techniques, including a relaxed environment, music therapy, time orientation, delivery instructions, and task completion motivation. The exercise task will focus on attention, organized thinking, and motor activities.

9. If you are in the traditional orientation method, you will be visited by a nurse at the start of each nursing shift. The nurse will ask you questions to check your memory and attention. Examples of questions include asking you for your name, the date, where you are, and what just happened to you. This will be repeated during every nurse shift change and is the usual care you would receive, even if you were not in the study. In this method, your vital signs (oxygen levels, how fast you are breathing, and your blood pressure) will be measured at different time points after your abdominal surgery as part of your standard care. When you wake up from surgery, you will have the traditional orientation questions asked of you until you are discharged from the hospital. Your participation in this study will be over after you leave the hospital.

Schedule of Activities

Procedures	Screening*	Day 1,	Day 1,	Day 1,	Day 1,	Post 24	Post 48	Post 72
		Time 1:	Time 2:	Time	Time	hours	hours	hours
		pre	10	3: post	4: end			
			minutes		of			
					study			
Visit number	Visit 0 or 1	Visit 1				Visit 2	Visit 3	Visit 4
Informed	X							
consent								
Demographics	X							
Medical history	X							
Randomization		X						
Administer			X-					
study								
intervention								
Concomitant	X							
medication								
review								

Page 9 of 21

Procedures	Screening*	Day 1, Time 1: pre	Day 1, Time 2: 10 minutes	Day 1, Time 3: post	Day 1, Time 4: end of study	Post 24 hours	Post 48 hours	Post 72 hours
Visit number	Visit 0 or 1	Visit 1				Visit 2	Visit 3	Visit 4
Physical exam (including height and weight)	X							
Frailty screening assessment	X							
Mini-Cog screening assessment	Х							
RASS Score	Х							
Pulse oximetry		X	Х	Х				
Respiratory rate		Х	Χ	Х				
Blood pressure		Х	Χ	Х				
System User Survey					Х			

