- Pain scores (using numeric pain rating scale tool)
- Safety adverse events

Identifier (or parts of)	Recorded	Disclosed	Comment
All elements of dates (except year) for dates	Yes	No	Necessary for complete data
directly related to an individual, including			analysis
patient names, birth date, admission date,			
discharge date, and date of death; and all			
ages over 89 and elements of dates			
(including year) indicative of such age			
Phone numbers; Fax numbers	Yes	No	Necessary to complete a
			questionnaire
Medical record numbers	Yes	No	Necessary to organize data
			collection

Page 12 of 21

Identifier (or parts of)	Recorded	Disclosed	Comment
Any other unique identifying number,	Yes	No	Virtual cognitive
characteristic, or code			interventions are frequently
			delivered

9. Data and Specimen Banking

No specimens will be obtained, stored, or banked in this study.

10. Study Population

This study will be a single-center study of older patients who underwent abdominal surgeries and will be conducted at Houston Methodist Hospital. We will enroll 30 patients scheduled to undergo abdominal surgery who are ≥60 years of age. The rationale for enrolling older patients is that older surgical patients are at high risk for the development of delirium.

A total of 30 patients will be prospectively enrolled. 15 patients will receive the standard of care / re-orientation technique, and 15 patients will receive ReCognitionVR-based cognitive exercises. All participants will be given post-use surveys to assess usability and acceptability outcomes.

Inclusion Criteria:

- 1. Patients ≥ 60 are scheduled to undergo the following abdominal surgeries (open or laparoscopic or robotic assisted) small bowel and large bowel surgery; cholecystectomy; Whipple procedure; pancreatectomy; splenectomy.
- 2. RASS Score 0

Exclusion Criteria:

- 1. Subjects with baseline cognitive impairment.
- 2. Person with active psychiatric disorders and being treated with medications, especially schizophrenia.
- 3. Person who is deaf or blind.
- 4. Person with an underlying cognitive disorder or associated phobias (e.g., claustrophobia).
- 5. Person participating in other clinical trials involving drugs, biologics, devices, or behavioral interventions.
- 6. Active seizure disorders.

11. Screening and Recruitment

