All participants will be screened by the PI and clinical research staff, who have been trained in the clinical investigational plan, to determine if the potential participant is eligible for enrollment. The screening for potential participants will be from within the PI's department. Potential participants will be assigned a screening number which is recorded in an Excel sheet; all participants who receive the study intervention will be noted. All participants must meet eligibility criteria (and if not, which eligibility criteria were not met will be recorded); reasons for not meeting enrollment criteria or receiving study intervention will be recorded. No participants belonging to a vulnerable population will be enrolled.

During the informed consent process, the investigator or designee, who has been trained on the protocol, will explain the nature and scope of the intervention, potential risks, and benefits of participation and answer questions from the potential participants. All participants will sign and date the Institutional Review Board (IRB)/Ethics Committee (EC) approved informed consent form before any study-specific procedures are performed. In addition, the signed informed consent will be retained with the research records, and a copy will be given to the participant.

Medical records will be reviewed for screening.

12. Withdrawal of Subjects

A participant may discontinue his or her participation without giving a reason at any time during the study. For example, the PI may withdraw a participant due to failure to comply with study intervention requirements, or the participant is uncooperative or refuses to continue in the study intervention. The data from these participants will be retained in the study file and analyzed.

Participants will be withdrawn from the study if they do not receive any study interventions. At the moment of withdrawal, all data related to the participant will be removed from the corresponding Excel documents and waivers will be shredded.

13. Provisions to Protect the Privacy Interests of Subjects

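### Section 5 and the Schedule of Activities disagree on whether randomisation comes before or after the Mini-Cog and RASS checks, so a VR patient's data can be removed after allocation while a comparable control stays

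*Combined protocol and SAP*

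**What the plan says.** Section 5 gives a numbered sequence. Step 2 reads "We will screen patients for inclusion and exclusion criteria and will assign a screening number". Step 3 follows: "After signing informed consent, participants will be enrolled in the study and randomized using computer-generated randomization software". The Mini-Cog then appears twice. Step 4 says "The experimental group will watch a video on using VR technology, placement of a VR headset, and assessment of baseline cognitive function using the Mini-Cog"; step 6 says "The Mini-Cog screening tool will assess the patient's cognitive status of all participants". Step 7, which describes the experimental group, gives the session after return from the operating room, once RASS is 0. Step 9, for controls, has no RASS check.

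The Schedule of Activities gives another order. The row "Mini-Cog screening assessment" is marked at Screening only, and so is the RASS row. Randomisation is marked at Day 1 Time 1. A footnote allows Screening and Day 1 to fall on the same day.

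In Section 10, RASS 0 is inclusion criterion 2, with no time point. Exclusion 1 is "Subjects with baseline cognitive impairment", with no instrument, cut-off or time point.

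Section 12 adds: "Participants will be withdrawn from the study if they do not receive any study interventions". It then has all data on such a participant removed. The paragraph before it keeps and analyses the data of participants who stop, or whom the investigator withdraws for non-compliance.

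**The concern.** A randomised comparison is protected only if eligibility is settled before allocation, or if what happens afterwards does not change who is counted. Section 5 as written secures neither. A check that can stop a participant from receiving the session comes after allocation, is described for one arm, and is followed by a rule that deletes those who received nothing.

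The two arms are not equally exposed to that rule. The VR session is a single event that depends on RASS 0. The control procedure is the nursing orientation that step 9 describes as usual care, so a control who is slow to recover still receives it and remains in the data. The patients at risk of deletion are those who recover slowly from anaesthesia. Their absence could affect the adverse event proportions, the 72-hour delirium count and, most directly, the feasibility proportion.

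**Working it through.** **Order of procedures, side by side**

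| Item | Section 5 | Schedule of Activities |
|---|---|---|
| Randomisation | Step 3, after consent | Day 1 Time 1 |
| Mini-Cog | Step 4 (experimental group) and step 6 (all), both after step 3 | Screening only |
| RASS | Step 7, after surgery, VR arm; absent from step 9 | Screening only; no Day 1 mark |

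The eligibility screen in step 2 does not settle the order. It precedes consent, and Section 11 allows study-specific procedures only after consent. Screening is described there as a review of medical records. If the Mini-Cog is a study procedure, it must follow consent, and Section 5 lists it after randomisation as well.

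For RASS, the Screening mark can refer to a pre-operative contact, because Section 18 identifies patients from the surgeon's clinic, the pre-anesthesia clinic and surgery lists. The score that step 7 needs is post-operative, and the Schedule has no mark for it in either arm unless Screening falls on that same day.

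**Path to deletion**

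1. The patient is randomised after consent (step 3).
2. The patient does not reach RASS 0 after surgery.
3. VR arm: no session is given (step 7), so Section 12 withdraws the participant and removes the data. Control arm: orientation continues (step 9), so the Section 12 rule is not triggered.

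**Size**

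Inputs from Section 4: 15 per arm (15 + 15 = 30) and a 70% feasibility target in the intervention group. The plan is descriptive and gives no alpha, power or dropout rate, so there is no sample-size calculation to reproduce.

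The target corresponds to 0.70 × 15 = 10.5 completers, so 10 of 15 misses it and 11 of 15 (73.3%) meets it. If k VR participants are removed, the proportion with 10 completers is 10/(15 − k). Intervals are 95% Clopper-Pearson:

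| Removed, k | Proportion | 95% interval |
|---|---|---|
| 0 | 10/15 = 66.7% | 38.4 to 88.2 |
| 1 | 10/14 = 71.4% | 41.9 to 91.6 |
| 2 | 10/13 = 76.9% | 46.2 to 95.0 |

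With 9 completers, three removals are needed: 9/15 = 60.0%, 9/13 = 69.2%, 9/12 = 75.0%.

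The documents give no rate at which VR patients fail to reach RASS 0. Assuming a rate f, equal and independent across patients, the expected number lost is 15f and the chance of at least one loss is 1 − (1 − f)^15:

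| Assumed f | Expected losses | Chance of at least one |
|---|---|---|
| 5% | 0.75 | 1 − 0.95^15 = 54% |
| 10% | 1.5 | 1 − 0.90^15 = 79% |
| 20% | 3.0 | 1 − 0.80^15 = 96% |

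**The case against.** The strongest reply is that the Schedule already has the right order. It marks the Mini-Cog and RASS at Screening and randomisation in the next column, and Section 11 requires every participant to be eligible. When Screening and Day 1 coincide, which the footnote and Section 18 allow, the RASS mark could itself be post-operative, before allocation and common to both arms. This is a possible reading, but Section 5 says otherwise, and nothing states which governs.

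A second reply is that step 7 says when the session is given, not who is excluded. The session could simply wait until RASS is 0. That also stands: no text excludes a patient who is not yet at 0. Deletion arises only if the patient never receives a session, and its frequency is unknown.

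Third, this is a small descriptive study in which Section 4 has each group evaluated separately, and delirium is exploratory. This limits the consequence for between-group claims. It does not protect the feasibility proportion, which is a single-arm figure. The objectives table sets that target for enrolled participants, which is hard to square with removing the data of some of them.

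A reader might also infer more than the documents support:

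- *The Mini-Cog is applied in the VR arm only.* Step 6 gives it to all participants. Step 4 is arm-specific wording, and can even be read as a list of what the video covers.
- *The Mini-Cog decides exclusion 1.* Step 4 describes it as "assessment of baseline cognitive function using the Mini-Cog screening tool", which makes the link plausible, but no text makes it. It may be a baseline descriptor, like the frailty screen.
- *The deletions would make VR look safer.* Losing slow-recovering patients from one arm could work that way, but the documents offer nothing to establish the direction or the amount.

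**Conclusion.** The point holds as an inconsistency with a real consequence. Section 5 and the Schedule give different orders for randomisation and the Mini-Cog. The post-operative RASS check is written for the VR arm, with no control counterpart and no Day 1 mark. Together with the data removal in Section 12, this permits one-arm deletion after allocation; it does not show that deletion will occur.

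One deletion changes the VR denominator by 1/15 = 6.7% and can carry the feasibility estimate across 70% (66.7% to 71.4%), although the intervals are wide and overlap almost entirely. The crossing at one deletion is specific to 10 completers. The 54% to 96% range rests wholly on the assumed failure rates of 5% to 20%, and on reading step 7 and Section 12 together as described. The correction should be made because it costs little and removes the ambiguity before data are collected.

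**What to change.** 1. Reconcile Section 5 with the Schedule so that the Mini-Cog, for all participants, and any other check used for eligibility come after consent and before randomisation. Take the Mini-Cog out of step 4.
2. State which assessment decides exclusion 1 and when. No cut-off or clinical rule is proposed here; that is for the sponsor.
3. Add a RASS mark at Day 1 Time 1 for both arms, so that the post-operative score already required by step 7 is recorded alike, and place randomisation after it in the same column, where the Schedule already puts it. Participants who do not qualify are then recorded as not enrolled, with the reason, as Section 11 provides.
4. Amend Section 12 so that every randomised participant stays in the analysis denominator, including anyone who receives no session, and the data are kept. This is still needed after step 3, because a participant can miss the session for other reasons.

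The cost is a few edited lines, one added mark in the Schedule and one RASS score per control. The small downside is that randomisation takes place at the post-operative visit.
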